## **Interventions Compared**

**TEAM** is a high-human touch, multidisciplinary SMH approach that connects participants with a personalized care team including gastroenterologists, advanced practice providers (APP)s, BH specialists, dietitians, registered nurses, pharmacists, and health coordinators who provide intensive support and resources for patients.

**TECH** is a low-human touch approach leveraging behavioral digital tools – primarily a digital cognitive behavioral therapy-focused mobile application with embedded health coaches – to deliver BH care at the patient's convenience.

## Study Design/Methodology

This multi-center study will involve an individual-level randomized design along with a pragmatic, mixed-methods approach to compare two existing care approaches, TEAM (high-human touch) and TECH (technology-supported care), for delivering IBD and behavioral health services to individuals with IBD within and SMH model. Participants will be actively enrolled in the study for 12 months. Study participants will receive care from the IBD SMH clinical team per usual care delivery processes established for TEAM and TECH for the duration of the study.

#### **Randomization Procedure**

Eligible participants who consent to participate in the study will be stratified by age (18-30, 31+), IBD disease activity (active/inactive), and IBD type (UC or Crohn's) which will be assessed at enrollment and before randomization to ensure that intervention arms are balanced with respect to these variables. The age cut-off of 30 was chosen because it includes the age-range patients are most often transitioned from pediatric to adult care; 18 is the age patients have the right to make their own health choices, and age 30 is usually when patients transition off their parents' health insurance. Within each stratum, random block sizes of two and four will be used to maximize balance between groups while minimizing the ability to unmask investigators to next treatment assignment, triggering an automated alert to staff on which approach to use.

We will monitor the randomization process throughout the study period to ensure there are no systematic differences between study arms and selection or assignment biases.

## Measures

#### **Primary outcomes**

IBD symptom severity will be captured from the IBD Complexity Composite Score which is a disease complexity grid developed for primary care patients that is used with IBD patients in order to quantify biological, psychosocial, and health system access domains of IBD, considering both history and current status so that integrated treatment can be personalized. It includes PROMIS GI symptoms scale, a self-report of breadth and depth of GI symptoms and Harvey Bradshaw Index (HBI) and Ulcerative Colitis Activity Index (UCAI), provider-rated scales for IBD disease activity. IBD disease activity will also be assessed using the PRO-2 disease severity index, which is a brief, recently validated patient-reported assessment for individuals with Chron's disease and ulcerative colitis.

Behavioral health symptom severity will be measured using scores from IBD Complexity Grid which uses the Patient Health Questionnaire Anxiety-Depression Scale (PHQ-ADS) – which combines the PHQ-8 and GAD-7 scales – as a composite measure of depression and anxiety. The Patient Health Questionnaire 8-item depression scale (PHQ-8) and 7-item Generalized Anxiety Disorder scale (GAD-7) are among the best validated and most commonly used depression and anxiety measures, respectively. The PHQ-ADS is the sum of the PHQ-8 and GAD-7.

#### **Secondary outcomes**

Functional impairment will be measured using the Short Form 12 Health Survey Version 2 (SF-12v2) which includes 12 items from the Short-Form 36 Health Survey and yields a physical and mental composite score as well as 8 subscale values: physical functioning, role-physical, bodily pain, general health, vitality, social functioning, role-emotional, and mental health. Lower scores correspond with poorer health-related functioning/quality of life.

IBD-IBS Symptom Severity. The Irritable Bowel Syndrome Symptoms Severity Scale (IBS-SSS) more accurately captures IBD symptom severity for many individuals with IBD, particularly those with inactive IBD but persistent functional GI symptoms (e.g., IBD-IBS). The IBS-SSS scores pain severity, pain frequency, abdominal bloating, bowel satisfaction and interference with life on a 0-100 scale with a total score of 500. A 50-point or more reduction in this score is considered clinically meaningful.

Health care utilization will be captured categorically via medical record data including ED visits and hospitalizations.

Patient engagement will be measured using the IBD Self-efficacy Scale which assesses one's confidence level in managing stress and emotions, managing medical care, managing symptoms and disease, and maintaining remission.

Quality of life will be measured using the Short Quality of Life in Inflammatory Bowel Disease Questionnaire (SIBDQ) $^{71}$ .

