## **Background and Significance**

Inflammatory bowel diseases, including Crohn's disease (CD) and ulcerative colitis (UC), are among the most costly gastrointestinal (GI) conditions in the United States (US) and are lifelong chronic diseases that, if not well managed, can significantly disrupt the lives of individuals. IBD afflicts three million U.S. patients and families with incidence rising globally, especially among younger age groups, during a critical social and career development period. IBD is a relapsing and remitting condition associated with varying degrees of GI inflammation (disease activity) and related symptoms of abdominal pain, diarrhea, nutritional deficits and fatigue. In the presence of anxiety and depression, IBD symptom load is even higher, even when inflammation is mild or absent. IBD carries a financial burden between \$14-31 billion annually in the U.S., with about 30% of adult IBD patients accounting for more than 80% of IBD-related healthcare spend; the largest drivers of cost are surgeries and hospitalizations, many of which are preventable. Prior studies have shown that medical utilization (both emergency department (ED) visits and unplanned hospitalizations) is driven by serious disease and IBD activity requiring steroids, biologics, or surgery, chronic unexplained pain and related opioid use, and unaddressed or undertreated behavioral health (BH) problems.

IBD patients exhibit higher rates of comorbid BH conditions, especially anxiety and depression, than healthy counterparts – these further compound disease complexity. Indeed, when present, BH issues directly and negatively impact medical/surgical treatment response, adherence to treatment regimens, care utilization including surgeries, and disease-related quality of life and functioning. Emerging adults with IBD are a large and uniquely vulnerable subpopulation who, if not effectively integrated into an adult-centered healthcare system, are at significantly higher risk for poor disease outcomes, Including high rates of anxiety and depression. Beginning in 2020, BH symptoms were further exacerbated by the COVID-19 pandemic, particularly for IBD patients who reported elevated levels of anxiety surrounding their vulnerability and concerns about securing needed care.

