## **Aims**

This study aimed to compare the effectiveness of two evidence-based, patient-centered behavioral approaches implemented within three existing medical homes: **TEAM**, a high-human touch multidisciplinary team-based approach delivered at point-of-care, and **TECH**, a low-human touch technology-based approach delivered at the patient's convenience with the guidance of health coaches. The study focused on patient-centered outcomes, impact on healthcare utilization, determining which intervention worked best for whom, and potential scalability of the model to other healthcare environments and for other chronic conditions.

**Primary Aim 1:** Examine the impact of TEAM vs. TECH on two main patient-centered outcomes of IBD and BH symptom severity and secondary outcomes of functional impairment, healthcare utilization, quality of life, and self-efficacy.

**Hypothesis 1:** Both TEAM and TECH approaches will result in clinically meaningful improvement across all outcomes.

**Primary Aim 2:** Examine the impact of patient characteristics on clinical response to TEAM or TECH approaches and establish subgroups of patients who will benefit most from each approach. The study focused on baseline IBD activity and age as primary moderators but secondarily explored site, IBD diagnosis, and health literacy.

**Hypothesis 2a:** The TEAM approach will show greater effects in those with active IBD, while TECH will show greater effects in those with inactive IBD.

**Hypothesis 2b:** The TECH approach will improve outcomes more in younger patients.

**Primary Aim 3:** Examine IBD patient and provider perspectives on facilitators and barriers to efficient and effective implementation of TEAM and TECH and the potential for scaling the interventions and SMH model to other common chronic diseases and community care settings to inform high-quality, efficient ongoing implementation and dissemination

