## **Statistical Analysis Plan**

## **Sample Size and Power Calculations**

The bundles of TEAM and TECH services have been tested as packages. For the TEAM approach, we evaluated the feasibility, durability, and impact of the IBD specialty medical home for 346 IBD patients after one year of enrollment. In the year following enrollment, there was a significant reduction in IBD disease activity for both UC (p=.0003) and CD (p=.002), unplanned care (both ER visits (p<.0001) and hospitalizations (p=.008), while there was an observed improvement in health-related quality of life (p<.0001), depression (p<.0001) and anxiety (p=.02). For the TECH approach, a combination of digital tools- an app based cognitive behavioral program, remote monitoring and telepsychiatry (TECH) was compared to behavioral treatment as usual (control) using a randomized trial prospective design for patients with IBD with anxiety and/or depression. There was a significantly greater reduction in anxiety in the TECH group over 3 months (delta 5.6); CI (3.9, 7.6); p<.0001; n=34) than in the control group (delta 2.5; CI (0.5, 4.6); p=.02; n=35. There was also a greater reduction in depression (delta 2.6 CI (0.6, 4.6); p=.01 in the active versus control group (delta=.0.4; CI (-2.2, 3.1); NS). 76 Ninety-six percent of patients in TECH group engaged with the digital CBT program and participated in remote monitoring with 69% completing a clinically meaningful number of sessions. Both studies were conducted in "real world" clinical setting and powerfully show how both approaches can provide powerful solutions in improving health care delivery in sustainable ways.

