Aim 1: We calculated statistical power for the target sample size of 675, with approximately 337 participants enrolled into both TEAM and TECH. After adjusting for the multiple testing in Aim 1 (2 tests) and considering 25% attrition, a sample size of 505 (approximately 252 per treatment group) will provide over 99.9% power for the hypothesis test for Aim 1. Among patients enrolled in the specialty medical home at that time who met active behavioral criteria (PHQ-4 >= 6), there was a significantly greater change in TECH (n=73; ES .49) versus TEAM (n=106; ES .36) for the behavioral composite but both approaches were associated with significant change over time (p=.005). Both approaches were also associated with significant improvement in the biological composite for both TEAM (ES .22) and TECH (ES .16). With the IBD SMH models of care being clinically operational at all three sites, we are collecting ongoing useful and robust information that has been published. In our most recent analyses of our clinical research registry tracking our TEAM approach (n=280), our most recent analyses show effect sizes comparable to these initial findings for both approaches.

Aim 2: We considered both subgroup analyses and formal tests of moderation. Subgroup analyses – Based on current data, our subgroups are relatively evenly proportioned. We expect that the smallest subgroup will be 42% of the sample and the largest will be 58% of the sample. Thus, our expected subgroup sizes after 25% attrition are between 212 and 293 for projected enrollment. For this range of subgroup Ns, we expect 0.80 power to detect small treatment effects ranging between 0.26 and 0.30. Moderation – We used Monte Carlo methods (100 runs) to simulate the binary moderator (M) and treatment (X) (both p=0.5), assuming M independent of X as expected in a randomized trial. Considering a range of effect sizes for B1, B2, and B3, we estimated the outcome Y as Y=B1\*X+B2\*M+B3\*X\*M+ $\varepsilon$ , where  $\varepsilon$ ^N(0,1). We averaged across

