Aim 1 will examine the impact of TEAM vs. TECH on the primary and secondary outcomes and will determine if changes in outcomes over time are different between the two groups. We will fit the GLMMs to associate each outcome with the intervention (TEAM vs. TECH) and other covariates of interest. To account for the within-patient correlation in longitudinal data and to reflect potential differences among three sites, we will add normally distributed random effects for patients and sites in addition to the fixed effects for intervention and covariates of interest. An inference of the intervention effects for each outcome will be carried out using Wald test based on the either F-distribution or Chi-square distribution as appropriate. For each outcome, the null hypothesis of homogeneous change in outcomes overtime between TEAM and TECH will be examined by testing the treatment-by-time interaction effect on each outcome. In the absence of significant interaction effects, the marginal difference in outcomes between TEAM and TECH will be examined using the same GLMMs without the interaction effect. All hypothesis tests for Aim 1 will be conducted at the overall significance level of 0.05. The score changes from baseline to each time point and their difference between TEAM and TECH will be estimated with 95% confidence intervals.

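### ED visits and hospitalizations are to be captured in undefined categories with no model named; counts analysed as rates would keep the frequency information at little cost

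*Combined protocol and SAP*

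**What the plan says.** Utilization is one of the Aim 1 outcomes. The Aims section lists it among the "secondary outcomes of functional impairment, healthcare utilization, quality of life, and self-efficacy" and also describes the study's emphasis this way: "The study focused on patient-centered outcomes, impact on healthcare utilization, determining which intervention worked best for whom". The Secondary outcomes section states that it "will be captured categorically via medical record data including ED visits and hospitalizations". That sentence is the whole definition. It gives no categories, cut-points, look-back window or per-patient summary.

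The Quantitative Analysis section applies one framework to everything: "We will fit the GLMMs to associate each outcome with the intervention (TEAM vs. TECH) and other covariates of interest". It names no distribution or link for utilization. The estimates it promises are changes in score from baseline to each time point, which have no clear meaning for a categorical variable. On duration, Study Design/Methodology says: "Participants will be actively enrolled in the study for 12 months".

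**The concern.** ED visits and hospitalizations are discrete events that can recur. The documents do not say that the medical record will yield their number and dates, but that is a reasonable inference from the source named. A coarse category drops part of that information. In the coarsest case, any versus none, one admission and several count the same, so fewer repeat encounters would not show as a difference. A category also takes no account of how long each patient's record was observed, whereas a rate model does.

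Three things are at stake: power for an outcome the study names as a focus, the ability to describe a change in frequency, and prespecification. With categories, window and model all open, they would have to be chosen later, possibly after the data have been seen, although the Quantitative Analysis section commits to analyses conducted as the plan describes.

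**Working it through.** **Inputs from the documents.** The plan has no utilization figure to reproduce: it gives no event rate, dispersion, effect size or power for this outcome. The earlier TEAM cohort is summarised by p-values only ("unplanned care (both ER visits (p<.0001) and hospitalizations (p=.008"). The per-arm number comes from the Aim 1 sample size statement, "a sample size of 505 (approximately 252 per treatment group) will provide over 99.9% power for the hypothesis test for Aim 1". As a check, 675 × 0.75 = 506, in line with the stated 505.

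**Assumptions (mine).** Counts are negative binomial with mean m per patient over the period and dispersion k (variance m + km²; k = 0 is Poisson). There is a common rate ratio of 0.7, equal follow-up, and a two-sided 0.05 test.

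**Formulas for any/none against counts.**
- Counts: Var(log rate ratio) = [(1/m + k) + (1/(0.7m) + k)]/n, and z = |ln 0.7|/√Var.
- Any/none: p = 1 − (1 + km)^(−1/k) in each arm, and z = (p₁ − p₂)/√{[p₁(1 − p₁) + p₂(1 − p₂)]/n}.
- Information lost = 1 − (z for any/none ÷ z for counts)².

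**Worked example: m = 1, k = 1, n = 252 per arm.**
- Counts: Var = (2 + 2.4286)/252 = 0.01757, SE = 0.1326, z = 0.3567/0.1326 = 2.69. Power = Φ(2.69 − 1.96) = 77%.
- Any/none: p₁ = 0.500, p₂ = 1 − 1/1.7 = 0.412, difference 0.088. SE = √[(0.2500 + 0.2422)/252] = 0.0442, z = 2.00. Power = Φ(2.00 − 1.96), about 51%.
- Loss = 1 − (1.996/2.691)² = 45%.

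**The same example at a low rate: m = 0.2, k = 1.**
- Counts: Var = (6 + 8.143)/252 = 0.0561, z = 1.51, power 32%.
- Any/none: p = 0.167 against 0.123, z = 1.40, power 29%.
- Loss = 13%.

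**Loss with any/none, in percent, rate ratio 0.7.**

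| Mean m | k = 0.5 | k = 1 | k = 2 |
|---|---|---|---|
| 0.1 | 4.8 | 6.6 | 10.0 |
| 0.2 | 10.2 | 13.3 | 18.5 |
| 0.5 | 23.9 | 28.6 | 35.3 |
| 1.0 | 40.8 | 44.9 | 50.4 |
| 1.5 | 52.6 | 55.2 | 58.8 |

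**Finer categories.** Here I used Fisher information for the log mean, which does not depend on the rate ratio. The full count carries m/(1 + km). A categorised count carries the sum over categories of (dp/d log m)²/p. For any/none this gives a loss of 1 − m/(eᵐ − 1) under Poisson and m/(1 + m) with k = 1.

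| Categories | Model | m = 0.5 | m = 1.0 | m = 1.5 |
|---|---|---|---|---|
| any/none | Poisson | 23% | 42% | 57% |
| any/none | k = 1 | 33% | 50% | 60% |
| 0/1/2+ | Poisson | 4% | 12% | 23% |
| 0/1/2+ | k = 1 | 11% | 25% | 36% |
| 0/1/2/3+ | Poisson | 0.4% | 3% | 7% |
| 0/1/2/3+ | k = 1 | 4% | 12% | 22% |

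The two methods differ by some points for any/none, because one is evaluated at a rate ratio of 0.7 and the other locally. They agree that the loss grows with the mean and shrinks as categories are added.

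**The case against.** The strongest reply is that the plan never says any/none. Capturing utilization categorically could mean 0/1/2+, 0/1/2/3+, or simply recording by type of encounter. On the last reading nothing need be lost. This stands, and it is why the loss is given for several readings.

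A reader might infer that the plan throws away a quarter to more than half of the utilization information. The documents do not support that as a fact. It requires the any/none reading and event rates that appear nowhere. By the Fisher calculation, a 25% loss needs a mean of at least 0.55 (Poisson) or 0.33 (k = 1), and a loss above 50% needs a mean above 1.26 or 1.00. ED visits and hospitalizations analysed separately could each be rarer than that.

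Two further inferences should be resisted. The background statement "about 30% of adult IBD patients accounting for more than 80% of IBD-related healthcare spend" concerns money, not numbers of visits, so it does not establish that repeat encounters are concentrated in a few patients. The planned 25% attrition is also not tied to record data: a patient who stops returning surveys may still have a complete record. How unequal record follow-up will be is therefore unknown.

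It is also fair to say that a proportion with any encounter is easy to interpret and robust to extreme users, that a GLMM can handle binary or ordinal outcomes, and that any/none loses less if treatment mainly changes whether any event occurs. These points justify keeping the proportion as a summary. They do not supply the missing definition or make the count analysis costly.

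**Conclusion.** The point holds in conditional form. The plan commits to a categorical capture, leaves the categories, window, distribution and link undefined, and nowhere provides for counts or for follow-up time. If encounters are collapsed, the loss ranges from near zero (fine categories, rare events) to more than half (any/none, mean above about 1). The any/none figures of 5% to 19% and 24% to 59%, and the powers of 77% and 51%, rest on negative binomial counts, a uniform rate ratio of 0.7 and equal follow-up. All three are assumptions, not figures from the plan. Using 252 per arm further assumes that the plan's attrition allowance applies to this outcome.

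This is an inexpensive improvement to a secondary outcome. It is not an error that threatens the trial's main conclusions.

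**What to change.** Define the window and, from the records already being read, extract for each patient the number of ED visits, the number of hospitalizations and the observed record follow-up over the 12 months. Analyse each count with a negative binomial mixed model within the existing GLMM framework, with log observed record follow-up as offset, and report a rate ratio with 95% confidence interval. Keep the any/none proportions by arm as a supporting summary.

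The cost is a few lines of SAP text and a slightly fuller extraction. The drawback is that a few very heavy users can move the rate ratio. The dispersion parameter widens the standard error but does not remove that influence, so prespecify a sensitivity analysis, for example with counts truncated at a stated maximum. If categories are kept instead, state them, the window and the link before the outcome data are examined.

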#### **Covariates**

Patient demographic and clinical characteristics will be obtained through existing clinical and administrative data on age, gender, race/ethnicity, insurance type, IBD age of onset, surgical history, and presence of ostomy.

e-health literacy will be measured using the eHealth Literacy Scale (eHEALS), which is an 8-item measure of eHealth literacy developed to measure consumers' combined knowledge, comfort, and perceived skills at finding, evaluating, and applying electronic health information to health problems.

Engagement in interventions will be assessed using automatically generated usage statistics, administrative/utilization data routinely collected for in-person visits, remote monitoring activity, and other intervention technologies. The integrity of care delivery for both approaches will be evaluated with existing checklists as part of weekly team huddles.

Resiliency will be measured using the Connor-Davidson Resilience Scale (CD-RISC 10), a validated, clinician-administered, EHR-integrated tool that quantifies, on a 100-point scale, an individual's personal strengths (high resiliency) vs. complexity (low resiliency).

Physical and behavioral health comorbidity will be assessed using the DSM-5 Cross-Cutting Symptom Measure which is an informant-rated measure that assesses current mental health domains across psychiatric diagnoses. ICD 10 codes will be used for current and past psychiatric diagnoses from initial SMH visit and past year ICD 10 codes for medical diagnoses.

Medications will include the use of psychotropic, opioid, and IBD medications.

Transition Readiness will be measured using the Transition Readiness Assessment Questionnaire (TRAQ), a self-reported assessment of health and skills needed for management of chronic disease and will evaluate patient readiness to change from traditional care to patient-centered care where patients and a provider team collaborate on treatment decisions.

Clinic/clinician characteristics will be assessed using clinician self-report years of experience and site-level patient load data. This information will be coupled with the "Engagement in interventions" variables described above.

